11.4.1 Dose storage

The following data will also be collected at each visit during the treatment phase (see Appendix 1) for study intervention storage information:

- where the study intervention is being stored (at the local health centre, the home of a participant in a refrigerator, the home of a participant in a cooler, or in a refrigerator at a neighbour's home). The final categories may be adapted to appropriately reflect the data collected.
- if refrigeration was off during storage (and how many doses were compromised).

Place of storage will be summarized using frequencies and percentages by treatment in a table for entire treatment period. A listing will be presented including place of storage, if refrigeration was off during storage, how long refrigeration was off, and number of doses compromised. This analysis will be presented for the Safety population.

11.4.2 Infant Feeding Diary Card

The IFDC captures information about the feeding the infant received on a particular study day through the Day 90 visit, which includes the following for each day:

- Number of breastmilk feedings
- Number of formula feedings
- Number of solid food feedings

Confidential Page 30 of 50

- Number of other feedings
- Total number of feedings

as well as info on whether or not the infant got all of the mixed study powder in, how the study powder was re-constituted and if vomiting occurred after administration of study intervention.

For each participant the proportion of feedings from breastmilk through the Day 56 Visit will be calculated as follows:

$$Prop\ breastmilk\ feedings = \frac{Sum\ of\ \#\ BM\ feedings\ per\ day}{Sum\ of\ \#\ Total\ feedings\ per\ day}$$

for available data up to Day 56 visit. Days with missing values in feeding information will not contribute to the above calculation.

The proportion of infants who had x% of feedings from breastmilk through the Day 56 visit will be summarized using summary statistics in a table by treatment according to the following categories:

- 100%
- 75% to 99%
- 50% to 74%
- 25% to 49%
- < 25%

A diary card entry on any given day is non-compliant, if no values were recorded for the feeding information and the total number of feedings for the day was missing. The proportion of infants who had x% of compliant entries will be presented by treatment group according to the following categories:

- 100%
- 75% to 99%
- 50% to 74%
- 25% to 49%
- < 25%.

Infant diary card results will be listed for the safety population. The listing will include whether diary card was returned, date of distribution, date of receipt, number of feedings for each type and the total.

11.5 Efficacy

11.5.1 Calculation of Weight-for-age z-score

WAZ is calculated at Screening and all clinical visits (Days 1, 28, 56, and 90).

The WAZ score is calculated in EDC using the approach defined by the WHO [2]. Given the weight (kg), sex and age (in days) of a participant, the WAZ is calculated as

Confidential Page 31 of 50

$$WAZ = \frac{\left(\left(\frac{Weight}{M}\right)^{L} - 1\right)}{L \times S}$$

where L, M, and S are pre-derived parameter estimates generated by the WHO. L, M, and S are conditional on the Sex and Age (days) of the infant. The lookup tables for the values of L, M, and S can be found on the WHO website [2]. Distinct tables for males and females are given.

WAZ is calculated directly in EDC and need not be derived. WAZ is rounded off to 2 decimals. The value for WAZ (at enrollment) after rounding off is used for randomization and defining the strata $(-3 < \text{WAZ} < -2, \text{WAZ} \le -3)$ (also used for study eligibility).

11.5.2 Primary outcome: CFB in WAZ at Day 56

11.5.2.1 Analysis of endpoint

WAZ will be summarized using descriptive statistics for actual and CFB values by visit and treatment group.

A MMRM will be used to estimate the difference in mean CFB between Bi-26 and Placebo, adjusting for covariates baseline WAZ, age (in days), country and discharge destination. The model will use CFB in WAZ as outcome and include the following effects:

- Fixed effects: Treatment, Visit (categorical), Treatment*Visit interaction, WAZ at baseline (continuous), Age (in days) at baseline, Country, Discharge destination
- Random intercepts: participant.

and will be fit using data from all planned follow-up visits where WAZ was measured, ie, Day 28, 56, and 90 visits. The adjusted interaction effects (Treatment*Visit) will be presented as estimates of the difference in CFB between treatment groups at each follow-up visit (Day 28, 56, and 90). The associated 95% CIs and p-values will be presented. PROC MIXED will be used to fit the models. SAS code for the models is provided in Appendix 3. If the WAZ score is not normally distributed, an appropriate transformation, such as the natural log, will be used as outcome for analysis. Normality will be investigated using q-q plots.

A participant listing of WAZ will be presented with actual values and CFB.

The descriptive table, model and listing will use the mITT population. The summary table will be repeated for the PP population.

Line graphs with the means and 95% CIs for WAZ will be presented by treatment group for visits Baseline, 28, 56, and 90.

Confidential Page 32 of 50

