4.2. Scientific Rationale for Study Design

Gut dysbiosis, or disrupted development of the gut microbiota, is hypothesized to be a contributing cause of infant malnutrition. Absolute *B. infantis* abundance is reported to be markedly lower in 3-to-24-month-old Bangladeshi infants and children under 24 months of age with SAM, compared to their healthy controls. The primary hypothesis to be tested in this study is Bi-26 supplementation for 28 days will lead to increased weight gain in underweight infants (WAZ <-2) who were hospitalized with acute non-surgical illness.

This study is designed as a double-blind, placebo-controlled study to enable equal attention and an unbiased evaluation of AEs and health outcomes.

WAZ was selected as the primary endpoint because it appears to be a better surrogate for mortality than WLZ [Mwangome 2019; Chowdhury 2021]. However, weight-for-age Z-scores require that the birth date of the infants enrolled is known and that weight is determined accurately.

We anticipate that an accurate gestational age at birth will often not be known for the infants enrolled. The study population will be heterogeneous and will include prematurely born infants and infants with normal weight-for-gestational age, infants with intrauterine growth retardation born small-for-gestational age, and infants with insufficient postnatal weight gain or weight loss due to illness and/or undernutrition.

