6.2. Measures to Minimize Bias: Randomization and Blinding

Randomization: On the day of hospital discharge (Visit 1, Day 1) participants will be randomized 1:1 to receive either Bi-26 or placebo. To minimize differences between Bi-26 and placebo groups within a given treatment arm, randomization will be stratified by:

- 1) country
- 2) age at enrollment (Study Day 1):30-59 days of age, 60-120 days of age
- 3) discharge destination (home, nutritional rehabilitation unit)
- 4) WAZ (≤ -3 versus > -3)

Target randomization is approximately 2/3 of participants with WAZ between -2 and -3 and approximately 1/3 with WAZ \leq -3. As such, a stratification blocking factor will be used in the ratio of 1:2 for (WAZ \leq -3):(-3 \leq WAZ \leq -2) within each treatment arm. Dynamic randomization will be utilized to balance the treatment groups for the other stratification factors.

Blinding: The study is double-blind. The placebo doses will be prepared to be as similarly as possible in appearance and odor to Bi-26. The final packaging material and the final target fill weight for Bi-26 and placebo will be identical. Study participants, principal investigators and study site personnel will remain blinded to treatment assignments throughout the study. The Gates MRI Medical Monitor, study monitors, and any other Gates MRI and contract research organization (CRO) personnel who are regularly in contact with the study site will remain blinded. Selected individuals listed below will have access to treatment allocations while the study is blinded:

- Biostatistician preparing the randomization list
- Biostatistician preparing the IDMC data
- IDMC members.

Additionally, in the event of a suspected unexpected serious adverse reaction (SUSAR), designated members of the sponsor or the sponsor representative's pharmacovigilance department may be required to unblind a study participant to meet country-specific reporting requirements.

Emergency unblinding: All participants will be centrally assigned to randomized study intervention using an Interactive Web Response System (IWRS). Before the study is initiated, the login information and directions for the IWRS will be provided to each site.

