8.1. Demographic and Baseline Characteristics

The following information pertaining to the participant will be obtained from the participant's mother at screening:

- Participant's sex, race, ethnicity, date of birth (including day, month, and year), and whether the delivery was a C-section.
- Participant's gestational age in weeks, if known, and the participant's birth weight (in kilograms). This information may be obtained from the hospital medical record if necessary.
- The mother's age will be obtained whenever possible.
- The participant's mother will be asked about breast-feeding practices from the time of the participant's birth, and planned feeding practices during the study (and this information will be captured in the case report form).

A full medical history and full physical examination will be performed at the screening visit (refer to Section 8.3.1). The participant's anthropometric measurements will be taken at the screening visit and at other specified timepoints in the SoA (refer to Table 2 and Section 8.3.1) for more details).

If the eligibility criteria are met, the participant will be enrolled into the study on Day 1. After enrollment, an estimation of socioeconomic status will be obtained if possible.

Hospital discharge to home, or to nutritional rehabilitation unit, will be collected on Day 1 and obtained from either the participant's parent(s)/legal guardian, or the hospital medical record. The anthropometric measurements obtained at Day 1 will be considered baseline for the purposes of statistical analyses (refer to Section 9.2).

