9.4. Primary Statistical Hypotheses and Sample Size Determination

The primary study hypothesis is that the difference in the mean change from baseline in WAZ is larger for participants randomized to at least 28 days of Bi-26 relative to placebo.

For the sample size calculation for the primary hypothesis, it is assumed that the between_group difference in the WAZ change from baseline is 0.45 with a standard deviation of 1.3. Based on the above assumption(s) using a 2-sided alpha of 5% and a power of at least 90%, a total of 354 participants, 177 in each group, is required.

Assuming a 10% loss to follow-up and a 3% mortality rate, a sufficient number of participants will be screened to ensure approximately 396 randomly assigned participants are enrolled, 198 in each treatment group.

Figure 2: Sample size sensitivity

N/group, 1-sided α =2.5%, Power=90%

9.5. **Populations for Analyses**

For purposes of analysis, the following populations are defined:

- Intention-to-treat (ITT) population: All participants randomly assigned to study intervention.
- **Modified intention-to-treat (mITT) population**: All participants randomly assigned to study intervention, who received at least one dose (including a partial dose) of the study intervention. Participants will be analyzed according to the intervention they were randomized.
- **Per-Protocol (PP) population**: All participants randomly assigned to study intervention, who received the study intervention, have a Day 90 visit, and did not substantially deviate from the protocol procedures. Participants will be analyzed according to the intervention they actually received. Details of criteria for defining the PP population will be specified in the Statistical Analysis Plan (SAP). The inclusion of participants in the PP population will be determined prior to unblinding the study. A participant data listing and a table with protocol deviations will be presented.
- **Safety population**: All participants randomly assigned to study intervention, who received any dose, including a partial dose, of the study intervention. Participants will be analyzed according to the intervention they actually received.

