11.6.5 Vital Signs

Vital signs, length (cm) and weight (kg) will be assessed and recorded at all clinic visits (Days 1, 28, 56, and 90). Vital sign measurements will include pulse rate (bpm), pulse oximetry (SpO2), and body temperature (°C). Measurements are to be repeated if clinically significant changes are observed or a machine error occurs. Body temperature should be taken per standard of care at the site. Length will be measured twice and both values will be recorded. The average value of the 2 recorded lengths will be used for any analysis.

A summary table with descriptive statistics for actual and CFB values, will be presented by visit and treatment group. PCI criteria for pulse rate, pulse oximetry (SpO2), and body temperature are given inTable 5.

Confidential Page 39 of 50

Table 5. Vital Signs PCI

Vital Signs Parameter	PCI Criteria
Body temperature	If temperature location is Axillary: < 36.5°C or > 37.5°C
	If temperature location is Ear: < 35.8°C or > 38.0°C
	If temperature location is Forehead: < 36.4°C or > 38.0°C
	If temperature location is Rectal: < 36.6°C or > 38.0°C
Pulse Rate	< 85 bpm or > 190 bpm
SpO2	< 95%

Temperature values should be rounded off to 1 decimal before applying PCI.

The number and percentage of participants meeting PCI for each vital sign (temperature, pulse rate, and pulse oximetry) at Day 28 visit and for any post-baseline visit will be summarized by treatment group in a table.

A participant listing of vital signs will be presented with actual values and a flag for values meeting PCI criteria.

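### The primary and key secondary models could gain precision by adding Day 1 length (with sex) and, optionally, birth weight, both already collected; this is an efficiency improvement, not an error.

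*SAP*

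**What the plan says.** Protocol 4.2 describes who will be enrolled: "The study population will be heterogeneous and will include prematurely born infants and infants with normal weight-for-gestational age". It goes on to name infants born small for gestational age, and infants with poor postnatal gain or with weight loss from illness or undernutrition.

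The primary mixed model in SAP 11.5.2.1 has treatment, visit and their interaction, plus "WAZ at baseline (continuous), Age (in days) at baseline, Country, Discharge destination". The key secondary model in SAP 11.5.3.1 is the same with baseline weight in place of baseline WAZ.

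Relevant baseline measures are already collected:

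- **Length.** The schedule of activities places it at screening and Day 1, and its footnote a puts Day 1 measurements before dosing. SAP 11.6.5 states: "Length will be measured twice and both values will be recorded"; their average is used. Length is summarised at baseline (SAP 11.2) and by visit (11.6.5), and it feeds WLZ (11.6.6).
- **Birth size.** At screening, Protocol 8.1 collects gestational age in weeks, "if known, and the participant's birth weight (in kilograms"). Birth weight appears only in the baseline summaries and listings of SAP 11.2.

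Neither length nor birth weight is a randomisation factor (SAP 7.2, 7.2.1), a listed subgroup (8.2) or a candidate in the confounder model (11.5.2.4.2). The one related analysis is SAP 11.5.2.4.3, which reruns the primary model with WAZ and age corrected for gestational age. Missing gestational age is not imputed there, and Protocol 4.2 expects an accurate value often to be unknown.

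**The concern.** Two infants of the same age and the same baseline WAZ can be quite different: one short because of small or early birth, the other thin after recent weight loss. Baseline WAZ and age cannot separate them; length and birth weight help to. If the two kinds regain weight at different rates after discharge, that difference stays in the residual variance of the primary contrast although the data to remove part of it are in hand.

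Adjusting for a measurement taken before randomisation does not bias the randomised comparison. If the measurement is prognostic, adjustment narrows the confidence interval and corrects for chance imbalance in a feature that the allocation algorithm does not balance. The choice has to be written down before unblinding; added later, it would look data-driven. What is at stake is some precision on the primary and key secondary results, not their validity.

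**Working it through.** **Inputs.** Protocol 9.4 assumes a "difference in the WAZ change from baseline is 0.45 with a standard deviation of 1.3", two-sided alpha 5% and power of at least 90%. It concludes that "a total of 354 participants, 177 in each group, is required". Allocation is 1:1 (Protocol 6.2). The documents do not say how strongly length or birth weight predicts WAZ change, nor whether 1.3 is an SD before or after covariate adjustment. The partial R² below is therefore an assumption, and its range starts at zero.

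**Step 1: the plan's own figure.** SE of the difference = SD × √(2/n) = 1.3 × √(2/177) = 0.1382, and 0.45 / 0.1382 = 3.26. The two-sample t-test (noncentral t) needs 176.35 per arm, rounded up to 177, with power 90.1% at 177. The plan's figure reproduces.

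**Step 2: effect of added covariates, taking 1.3 as the residual SD after the planned covariates.** Let R² be the share of that residual variance explained by the added measures. New SD = 1.3 × √(1 − R²); relative fall in SE = 1 − √(1 − R²); equivalent n per arm = 177 / (1 − R²).

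| Assumed R² | SD | Fall in SE | Power at 177 per arm | Equivalent n per arm |
|---|---|---|---|---|
| 0 | 1.300 | 0 | 90.1% | 177 |
| 0.05 | 1.267 | 2.5% | 91.5% | 186 |
| 0.10 | 1.233 | 5.1% | 92.8% | 197 |
| 0.15 | 1.199 | 7.8% | 94.1% | 208 |

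**Step 3: if 1.3 is the unadjusted SD.** The planned covariates then already reduce it. The percentage fall in SE from the added covariates is unchanged, but power starts higher and has less room to rise. Assuming that the planned covariates explain 10%, power starts at 92.8%; a further 5% of the remainder gives SD 1.3 × √(0.90 × 0.95) = 1.202 and power 94.0%, a gain of 1.2 points. Assuming 20%, power goes from 95.3% to 96.1%, a gain of 0.8 points. The corresponding gain in Step 2 is 1.4 points.

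**Step 4: cost if the covariate is useless.** In 4,000 simulated trials of 354 infants analysed by ANCOVA, adding a covariate with R² = 0 and no missing values moved the mean SE from 0.1382 to 0.1384.

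**Step 5: missing values.** This matters for birth weight, whose completeness is unknown. In the same simulation with R² = 0.10 and an assumed 30% missing, dropping incomplete infants cut power to about 81%. A simple fill plus a missing-value indicator kept it at about 92%. With 60% missing the figures were about 58% and 91%.

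These calculations use a single-time-point comparison, not the planned three-visit mixed model, so they indicate the order of the gain only.

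**The case against.** The strongest reply is that nothing is broken. The model covers all four randomisation factors, with WAZ and age as continuous terms. The estimand tables (Protocol Table 4, SAP Table 1) ask for stratification factors and feeding regimen covariates, so leaving out length and birth weight breaks no promise in the protocol. Planned power is met without them. All of this stands, and it is why the point is an improvement rather than a correction.

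Second, the premise that these infants recover differently is not in the documents. Protocol 4.2 lists who will be enrolled; it says nothing about their later WAZ course, or about what length adds once baseline WAZ and age are known. This also stands. A reader might infer from Protocol 4.2 that precision is certainly being lost; the text does not support that, and the true gain could be zero.

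Third, the plan does not ignore this heterogeneity. Length is reported by visit and through WLZ, and the analysis in SAP 11.5.2.4.3 addresses prematurity directly. That is a partial answer: it is a sensitivity analysis, it is limited to infants with a known gestational age, and it uses neither length nor birth weight as a covariate.

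Fourth, raw length depends on sex. WAZ is sex-standardised but sex is not in the model, so length alone would partly stand in for sex. That is right, and the fix includes sex for this reason.

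**Conclusion.** The point holds as an optional gain in efficiency. The primary and key secondary models use neither Day 1 length nor birth weight, although both are collected and Protocol 4.2 names the heterogeneity that they would help describe. For an assumed partial R² of 0 to 15%, the gain runs from nothing to a 7.8% smaller SE, or from 90.1% to 94.1% power at 177 per arm, if 1.3 is the residual SD; the power gain is smaller if 1.3 is unadjusted. It rests on prognostic strength that the documents do not give.

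A reader might go further and conclude that the primary analysis is biased or underpowered for want of these terms. The documents do not support that: randomisation protects the comparison, and the stated sample size reproduces without them. The case for the change is an asymmetry. It costs almost nothing if length is not prognostic and helps if it is. That argument is clean for length, which is scheduled for every infant on Day 1, and weaker for birth weight, which may be incomplete.

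**What to change.** Before unblinding, amend SAP 11.5.2.1 and 11.5.3.1 to:

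1. Add Day 1 length (mean of the two readings) as a continuous covariate, together with sex. Length is preferable to WLZ, which SAP 11.6.6 sets to missing below 45 cm.
2. Optionally, add birth weight with a simple fill, made without regard to treatment arm, and a missing-value indicator, so that no infant is dropped. Gestational age is better left to the existing sensitivity analysis because it will often be unknown.
3. Keep the currently listed model as a supporting analysis, and state which covariate set applies in the analyses that refer back to 11.5.2.1.

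If the sponsor prefers the present model, a sentence giving the reason would settle the matter.

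The cost is a short SAP amendment, a few degrees of freedom and a missing-value rule for birth weight. No new data are needed.

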6.2 Secondary Objectives

Table 2. Secondary Objectives

Objective		Estimand
Key Secondary		
To evaluate the change in weight of	a)	Population : The mITT population will be used for this analysis.
infants receiving Bi-26	b)	Endpoint : weight change (in grams) from baseline (Day 1) to the Day 56 visit in Bi-26 group.
	c)	Population level summary : Mean change from baseline in weight in the Bi-26 group compared to placebo with stratification blocking factors and feeding regimen covariate(s).
	d)	Intercurrent event(s): Including but not limited to treatment discontinuation.
Secondary		
To estimate the treatment response over time associated with Bi-26	a) b)	Population : The mITT population will be used for the analysis. Endpoint : WAZ change from baseline (Day 1) over time through the Day 90 visit (longitudinal assessment) by duration of dosing.
	c)	Population level summary : Mean change from baseline in WAZ over time in the Bi-26 group compared to placebo with stratification blocking factors and feeding regimen covariate(s).
	d)	Intercurrent event(s): Including but not limited to treatment discontinuation.
To assess the proportion of infants	a)	Population : The Safety population will be used for the analysis.
who achieve a specified change in WAZ from baseline to Day 56	re a specified change in b)	Endpoint : Proportion of infants with $a \ge 0.3$, 0.4, and 0.5 change in WAZ from baseline (Day 1) to Day 56 visit.
	c)	Population level summary : Frequency and percentages of infants with a ≥ 0.3 , 0.4, and 0.5 change in WAZ from baseline (Day 1) to Day 56 in the Bi-26 and placebo groups.
	d)	Intercurrent event(s): Including but not limited to treatment discontinuation.

Confidential Page 11 of 50

To assess the proportion of infants who achieve a specified WAZ at Day 56

- a) **Population**: The Safety population will be used for the analysis.
- b) **Endpoint:** Proportion of infants with a WAZ > -2 at Day 56 visit.
- c) **Population level summary:** Frequency and percentages of infants with a WAZ > -2 at Day 56 in the Bi-26 and the placebo groups.
- d) **Intercurrent event(s)**: Including but not limited to treatment discontinuation.

To assess the re-hospitalization rate

- a) **Population**: The Safety population will be used for the analysis.
- b) **Endpoint:** Number of re-hospitalizations for acute non-surgical illness through the Day 56 visit.

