7.1.3 Justification of Sample Size

[figure not shown]
The primary study hypothesis is that the difference in the mean change from baseline in WAZ is larger for participants randomized to at least 28 days of Bi-26 relative to placebo.

For the sample size calculation for the primary hypothesis, it is assumed that the between group difference in the WAZ change from baseline in 0.45 with a standard deviation of 1.3. Based on the above assumption(s) using a 2-sided alpha of 5% and a power of at least 90%, a total of 354 participants, 177 in each group are required.

Confidential Page 14 of 50

Assuming a 10% loss to follow-up and a 3% mortality rate, a sufficient number of participants will be screened to ensure approximately 396 randomly assigned participants are enrolled, 198 in each treatment group.

Figure 2. Sample size sensitivity

N/group, 1-sided $\alpha = 2.5\%$, Power=90%

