8.1.5 Per-Protocol (PP) Population

All participants randomly assigned to study intervention, who received the study intervention, have a Day 90 visit, and did not substantially deviate from the protocol procedures. Important protocol deviations will be evaluated individually by the sponsor to decide whether it has basis to exclude a participant from the PP population. Deviation from study intervention compliance (see Section 11.4) is defined as compliance of less than 80%. Participants will be analyzed according to the intervention they actually received (for details refer to Section 11.1).

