10 OVERALL STATISTICAL CONSIDERATIONS

10.1 General Conventions

Descriptive statistics will be presented for continuous data with applicable decimal precision as follows in relation to the source data (indicated as N+x), with a maximum of 3 decimals to be displayed:

- Number (N).
- Mean, (N+1).
- Number of missing observations, (N).
- Standard deviation (SD), (N+1).
- Median, (N+1).
- Minimum, (N+1).
- Maximum, (N+1).

Absolute and relative frequencies will be used to describe categorical variables. Unless otherwise specified, the denominators for percentages will be the number of participants in each intervention group with non-missing data for the variable of interest at the summarized visit. Percentages will be presented with 1 decimal place and a percent sign (%).

All statistical testing will be 2-sided and performed at the 0.05 level. When reporting the results of significance tests p-values will be reported. All confidence intervals will be 2-sided at the 95% level, unless otherwise stated.

Study day is calculated relative to the first study intervention administration on Day 1.

Confidential Page 22 of 50

- If the current ACR date is after study intervention administration: Study Day = (Current ACR Date – Study Intervention administration Date) + 1
- If the current ACR date is before study intervention administration:

Study Day = (Current ACR Date – Study Intervention administration Date)

Study day will not be calculated if either the current ACR or the study intervention administration date is incomplete or missing.

The following periods for the study are defined:

- Treatment Period: Day 1 through last dose of participant.
- Follow-up Period: Day of last dose of participant + 1 up to EoS.

SAS® code of SAS® procedures that will be used to perform efficacy and safety analyses is provided in Appendix 3.

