11.5.3.1 Analysis of endpoint

Weight (grams) will be summarized using descriptive statistics for actual and CFB values by visit and treatment group. CFB values will be presented in the summary table in gram units. To obtain CFB in grams, weight (kg) as captured in the eCRF will be multiplied by 1,000.

The same model presented in Section 11.5.2.1 will be used to estimate the difference in mean CFB (in grams) between Bi-26 and Placebo at Day 56, adjusting for baseline weight (grams), age, country, and discharge destination. The adjusted interaction effects (Treatment*Visit) will be presented as estimates of the difference in CFB between treatment groups at each follow-up visit (Day 28, 56, and 90). The associated 95% CIs and p-values will be presented. PROC MIXED will be used for the analysis. Normality will be investigated using q-q plots. If weight is not normally distributed an appropriate transformation, such as the natural log, will be used as outcome for analysis.

A participant listing of weight will be presented with actual values (in kilograms and grams) and CFB (in grams).

The descriptive table, model and listing will be presented for the mITT population. The summary table will be repeated for the PP population.

Confidential Page 34 of 50

Line graphs with the means and 95% CIs for weight (grams) will be presented by treatment group for visits Baseline, 28, 56, and 90.

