11.5.4 Secondary outcome: Change over time in WAZ by duration of dosing

11.5.4.1 Analysis of endpoint

The difference in the change over time will be represented as the estimated difference in CFB at Day 90 using the results generated by the model as described in Section 11.5.2.1 for the PP population.

In order to take duration of dosing into account, the model described above will be adjusted by study intervention compliance (see Section 11.4) and presented in separate tables for the mITT and PP populations.

11.5.5 Secondary outcome: Proportion of infants with increase in WAZ ≥ 0.3 , 0.4 and 0.5 at Day 56

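### The primary repeated-measures model has only a participant random intercept, so it assumes one variance for WAZ change at Days 28, 56 and 90; if spread differs by visit, its confidence intervals are miscalibrated

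*SAP*

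**What the plan says.** SAP 11.5.2.1 fits change from baseline in WAZ at Days 28, 56 and 90 in one PROC MIXED model. The fixed effects are treatment, visit, their interaction, baseline WAZ, age, country and discharge destination. The within-participant part is given as "Random intercepts: participant". The section names no residual covariance structure, no variance by visit, no robust standard error and no degrees-of-freedom method. It promises a treatment difference, 95% CI and p-value at each of the three visits.

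The model is used again in several places:

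- In 11.5.3.1 it gives the key secondary outcome, weight in grams.
- In 11.5.4.1 the change over time "will be represented as the estimated difference in CFB at Day 90 using the results generated by the model", in the per-protocol (PP) population. SAP Table 2 says of the same endpoint "The mITT population will be used for the analysis".
- In 11.5.2.4.1 to 11.5.2.4.3 the sensitivity analyses keep the same model.

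The only model comparison described is for an optional site random effect (10.5). The by-visit table would show unequal spread: "WAZ will be summarized using descriptive statistics for actual and CFB values by visit and treatment group", and SD is among the statistics listed in 10.1. No rule says what to do if spread is unequal.

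The SAS code is said to be in Appendix 3. Only Table 8 of that appendix is legible in the text available here.

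**The concern.** A participant random intercept plus independent residual error gives every visit the same total variance and every pair of visits the same covariance. When there are no missing data, the standard error at each visit then uses the average of the three visit variances, whatever the true variance is at that visit. If the spread of WAZ change differs over the 90 days, the interval is too narrow at visits with above-average spread and too wide at the others.

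The Day 90 secondary estimate and the Day 28 estimates are the most exposed. The by-visit SDs may reveal the problem, but a covariance changed after unblinding would be a post hoc choice.

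A smaller, separate mismatch sits in the same model. The primary estimand (Protocol Table 4, SAP Table 1) includes feeding regimen covariates. The primary model contains none, and SAP Section 9 does not list this as a change from the protocol. The main point does not depend on it.

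**Working it through.** **Inputs.** The difference is 0.45, the SD 1.3, two-sided alpha 5% and power at least 90%, with 177 per group (Protocol 9.4, SAP 7.1.3). Attrition comes from the same SAP section: "Assuming a 10% loss to follow-up and a 3% mortality rate". SDs by visit are not given, so those below are assumptions.

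**The plan's own figure.** The normal approximation gives n = 2 × (1.960 + 1.282)² × 1.3² / 0.45² = 175.4, so 176 per group. The t-based calculation gives 177 (power 0.901), which reproduces the plan. By the normal approximation, power at 177 is 90.3%.

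**Formula, complete data.** For visit v,

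SE ratio (model / true) = √(mean of the three visit variances / variance at v)

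type I error = 2 × [1 − Φ(1.96 × SE ratio)]

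Between-visit correlation cancels.

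**Worked example.** SDs 1.2/1.3/1.4 have variances 1.44, 1.69 and 1.96, with mean 1.697. At Day 90 the ratio is √(1.697/1.96) = 0.930, and the type I error is 2 × [1 − Φ(1.824)] = 6.8%.

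**Without assuming a pattern.** A visit whose SD is 5, 10 or 20% above the root-mean-square SD of the three visits has type I error 6.2, 7.5 or 10.2%. At 5, 10 or 20% below, it is 3.9, 2.9 or 1.4%.

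**Illustrative patterns (Day 28/56/90).** Elapsed days from the Day 1 baseline are 27, 55 and 89.

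| Assumed SDs | SE ratio | Type I error (%) |
|---|---|---|
| 1.3/1.3/1.3 | 1/1/1 | 5.0/5.0/5.0 |
| 1.2/1.3/1.4 | 1.085/1.002/0.930 | 3.3/5.0/6.8 |
| 1.12/1.30/1.49 (half of Day 56 variance constant, half growing with days) | 1.169/1.009/0.882 | 2.2/4.8/8.4 |
| 0.91/1.30/1.65 (variance proportional to days; extreme) | 1.453/1.018/0.800 | 0.4/4.6/11.7 |
| 1.4/1.3/1.2 | 0.930/1.002/1.085 | 6.8/5.0/3.3 |
| 1.5/1.3/1.1 | 0.873/1.008/1.191 | 8.7/4.8/2.0 |
| 0.9/1.3/1.3 (rise, then plateau) | 1.313/0.909/0.909 | 1.0/7.5/7.5 |

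In the three rising cases the Day 90 interval is 7, 12 and 20% too narrow. With 1.5/1.3/1.1 the Day 28 interval is 13% too narrow and the Day 90 interval 19% too wide. Over all the steadily rising or falling cases run, Day 56 type I error lies between 4.4 and 5.2%. Day 56 power falls by at most 0.6 points, from 90.3 to 89.6% after rounding.

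**Population.** PP members must "have a Day 90 visit, and did not substantially deviate from the protocol procedures", so the complete-data formula suits 11.5.4.1 as written. For mITT, 10% + 3% = 13% were removed completely at random. Since the timing is not given, all loss was placed before Day 28, between Days 28 and 56, or between Days 56 and 90, with equal correlation 0.5, 0.7 or 0.9. Day 90 type I error is then 6.8–7.1%, 8.4–8.9% and 11.7–12.9% in the three rising cases. Day 28 with 1.5/1.3/1.1 gives 8.15–8.69%.

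**Simulation.** With 177 per group, complete data, no true effect and 20,000 trials per setting, random-intercept rejection rates were within 0.35 points of the formula. Visit-specific variances gave 4.6–5.3% at every visit. A second simulation (198 per group, dropout building up to 13%, 1,500 trials per setting) gave random-intercept coverage at Day 90 of 0.916 for SDs 1.1/1.3/1.5 and 0.896 for 1.0/1.3/1.6. For 0.9/1.3/1.3, Day 56 coverage was 0.915. Unstructured covariance gave 0.941–0.959 at all visits in every setting.

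**The case against.** The strongest objection is that the deciding text cannot be read. The SAP points to Appendix 3 for its code, and a REPEATED statement with visit-specific variances may be there. That stands as a limit: the point is about the prose of 11.5.2.1. If the code does free the variances, prose and code describe different models and must still be aligned.

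Second, there is no evidence that the spread is unequal. WAZ is already standardised for age, and with equal SDs there is no error. That is also true. But equal variance is an assumption the analysis does not need, and the plan neither justifies it nor checks it.

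Third, Protocol 9.6 plans a blinded review of the analysis, when SDs pooled over arms could be examined. Its listed topics are outliers, violators and exclusions; covariance is not among them, and the SAP gives no rule to apply. The SAP's one data-driven change to this model's outcome, a transformation, answers non-normality.

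Fourth, the primary and key secondary outcomes are both at Day 56, which the steady patterns barely affect, and the SAP sets no confirmatory testing sequence for Days 28 and 90. This does limit what is at stake. No gram-scale calculation was made. However, the protection at Day 56 depends on its SD lying near the average of the three visits. The plateau case shows that it can fail.

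**Conclusion.** The concern holds for the model as the prose states it. It is conditional on SDs differing by visit, in either direction, and on the unread code not already allowing this. A visit with spread 10% above the three-visit root-mean-square would be tested at about 7.5% instead of 5%. At 20% above, the level is about 10%. The clearest exposure is the Day 90 secondary estimate and the Day 28 estimates. The Day 56 primary is essentially unaffected under a steady rise or fall, but would have about 7.5% type I error if SDs were 0.9/1.3/1.3. The sample size is unaffected. This should be corrected before unblinding; confidence is medium because the visit SDs and the code are unknown.

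**What to change.** In SAP 11.5.2.1, and hence in 11.5.3.1, 11.5.4.1 and the sensitivity analyses that reuse the model:

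- Replace the random intercept with an unstructured within-participant covariance by visit (in PROC MIXED, `REPEATED visit / SUBJECT=participant TYPE=UN`). With three visits this already saturates the covariance, so the random intercept should be removed and not kept alongside it.
- Pre-specify one heterogeneous-variance fallback for non-convergence and a degrees-of-freedom method. The choice of each is the sponsor's.
- Make the Appendix 3 code match. If it already does this, correct the prose.

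Separately, reconcile estimand and model on feeding. Either add the pre-randomisation feeding category already collected (11.2), or remove feeding from the estimand and record that in Section 9. The breastmilk proportion through Day 56 is measured after randomisation and should stay out of the primary model.

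The cost is a few lines of text and a code check. The unstructured matrix has six parameters for three visits and about 396 infants, and no new data are needed.
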